#### 8.1.3 Analyses of secondary efficacy endpoints

All secondary efficacy analyses will be exploratory, i.e. performed without adjustment for multiplicity, using standard methods of inferential statistics appropriate for the given secondary outcome measure. Two-sided tests for detecting treatment differences will be carried out.

Descriptive comparisons of, e.g. change scores measured at T1 and T2, or patient characteristics, will be mainly conducted with the t-test or Mann-Whitney-Wilcoxon test or, in the case of a binary outcome, with the Fisher's exact test, as appropriate based on distribution characteristics. With respect to missing score values, the same considerations used for the primary outcome will apply equally to the pre-specified secondary efficacy outcomes.

Secondary outcomes will be used to explore sociodemographic and behavioral determinants of the study outcome throughout the observation period as well as their interaction with the intervention. Sub-studies will explore trajectories of secondary outcomes throughout the study period, as well as

the impact of the intervention on these outcomes, e.g. health-related quality of life, depression, healthcare utilization. Adjusted multivariate regression models (e.g. mixed effect models for longitudinal data, GLM for cross-sectional data) will be chosen based on the available data and distributions for further exploratory analyses of secondary outcomes. Qualitative studies will assess process indicators in order to evaluate applicability and feasibility of the proposed intervention.

#### Health economic evaluation

The cost-effectiveness of the NET intervention compared to iTAU will be determined from a societal perspective based on the ITT population. First, the incremental cost-effectiveness ratio (ICER) will be calculated as the difference in mean cost divided by the difference in mean QALYs:

ICER= (CostNET - CostsiTAU)/(QALYNET - QALYiTAU).

Second, net-benefit regressions will be conducted to determine the uncertainty of the point estimate (ICER) and to adjust for potential baseline differences and confounders (Hoch 2002). These results will be used to construct cost-effectiveness acceptability curves, which show the interventions' probability of being cost-effective at different willingness-to-pay margins (Range: 0€/QALY − 150.000€/QALY; raised in 10.000€/QALY steps) in comparison to iTAU. The underlying assumptions regarding the calculation of costs and benefits will be investigated in several sensitivity analyses.

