#### 7.1.7 Questionnaires for the health economic evaluation

The efficacy outcome of "PICTURE-Economics" is the *incremental cost-effectiveness ratio*. To assess the incremental cost-effectiveness ratio, two measures, one for costs, one for effects, are necessary.

Costs will be assessed by means of a modified (shortened) German version of the Client Sociographic and Service Receipt Inventory (CSSRI) (Chisholm et al., 2000). This questionnaire considers the resource utilization for inpatient services, outpatient physician services, outpatient therapeutic services, medications as well as formal and informal care. Additionally, the questionnaire captures productivity losses caused by absenteeism. Resource utilization will be monetarily valued by means of administrative and market prices according to the German manual for standardized unit costs by Bock et al., 2015). Absenteeism will be valued according to the human capital approach by means of gross hourly wage plus non-wage labor costs.

**QUALYs**: As measure of effects, we will use QALY, a composite measure consisting of the duration of life multiplied by a measure of preference-based HRQoL. In this study, the EQ-5D-5L index values will be employed (Herdman et al., 2011).

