The cost-effectiveness of the NET intervention compared to iTAU will be determined from a societal perspective based on the ITT population. First, the incremental cost-effectiveness ratio (ICER) will be calculated as the difference in mean cost divided by the difference in mean QALYs:

$$\text{ICER} = (\text{Cost}_{\text{NET}} - \text{Costs}_{\text{iTAU}}) / (\text{QALY}_{\text{NET}} - \text{QALY}_{\text{iTAU}}).$$

Second, net-benefit regressions will be conducted to determine the uncertainty of the point estimate (ICER) and to adjust for potential baseline differences and confounders (Hoch 2002). These results will be used to construct cost-effectiveness acceptability curves, which show the interventions' probability of being cost-effective at different willingness-to-pay margins (Range: 0€/QALY – 150.000€/QALY; raised in 10.000€/QALY steps) in comparison to iTAU. The underlying assumptions regarding the calculation of costs and benefits will be investigated in several sensitivity analyses.

Further methodological detail will be included in a separate section of the Statistical Analysis Plan (SAP) of the principal trial. The impact of incomplete documentation with respect to the applied CSSRI and EQ questionnaires will be discussed as well.

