12.6.2 T0 (Baseline visit, Enrolment)

At baseline visit T0, 3 month after T -1 (+/- 2 weeks), the GP will finally check the patient's inclusion and exclusion criteria (i.e. **final confirmation of eligibility**, screening instrument: MoCA). Furthermore, baseline data collection during this face-to-face visit will be performed. This also includes the completion of self-administered questionnaires (PDS-5, PHQ-9, OASIS, PAM, WHODAS 2.0 , EQ-5D-5L, CSSRI).

A follow-up appointment to be scheduled after randomization will be determined.

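### The ICER is computed from unadjusted means, while its acceptability curve comes from regressions meant to adjust for baseline: both should use one named covariate set

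*SAP*

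**What the plan says.** SAP 8.1.3, under Health economic evaluation, sets out two steps, both in the ITT population and from society's perspective.

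- The point estimate: "the incremental cost-effectiveness ratio (ICER) will be calculated as the difference in mean cost divided by the difference in mean QALYs". The formula contains only arm means of cost and QALYs.
- Its uncertainty: "net-benefit regressions will be conducted to determine the uncertainty of the point estimate (ICER) and to adjust for potential baseline differences and confounders". The text continues: "These results will be used to construct cost-effectiveness acceptability curves", on a willingness-to-pay grid from 0 to "150.000€/QALY; raised in 10.000€/QALY steps".

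Protocol 5.2.2 has the same plan, including "the difference in mean cost divided by the difference in mean QALYs". It also promises further methodological detail in a separate SAP section, but the SAP repeats the protocol's analysis text and names no covariates.

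SAP 7.1.7 makes the ICER the efficacy outcome of PICTURE-Economics. On the utilities it says: "In this study, the EQ-5D-5L index values will be employed". It does not say how the T0 value enters the QALY. Both instruments are available at baseline: protocol 12.6.2 lists among the T0 procedures the "completion of self-administered questionnaires (PDS-5, PHQ-9, OASIS, PAM, WHODAS 2.0 , EQ-5D-5L, CSSRI"), and the SAP's schedule of assessments agrees.

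**The concern.** The second step is meant to describe the uncertainty of the first, but the two steps need not use the same estimator. The ICER has no covariates; the regressions behind the curve are described as adjusting. Neither document specifies an adjusted ICER or an unadjusted curve to go with the unadjusted ICER.

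Two things are at stake. The point estimate forgoes precision that data already collected at T0 would give. And if the arms differ by chance in baseline utility, a reader may find an ICER in the report that does not sit where the curve crosses 50%, with no explanation in the plan. Because the covariates are unnamed, the adjusted result also depends on choices made after the data are seen.

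**Working it through.** **Inputs from the documents.** 318 randomized (SAP 4.1) at 1:1 (SAP 6), so about 318/2 = 159 per arm. EQ-5D-5L at T0, T1 (6 months) and T2 (12 months). The documents give no utility SD, correlation between visits, cost variance or expected QALY gain, so there is no planned economic figure to reproduce.

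**Assumptions.** Utility SD 0.25 at every visit, a common correlation r of 0.4 to 0.6 between visits, complete data.

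**Step 1: where the curve crosses 50%.** At willingness-to-pay λ, incremental net benefit is λ·ΔQ − ΔC. With linear models and the same covariates at each λ, it is zero at λ = ΔC/ΔQ, with both differences taken from that model. An unadjusted regression therefore crosses at the unadjusted ICER and an adjusted one at the adjusted ICER. This needs no assumed figures.

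**Step 2: precision if T0 enters by the trapezoid rule.** QALY = 0.25·U0 + 0.5·U1 + 0.25·U2. Then:

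- variance = SD²·(0.375 + 0.625r)
- covariance with U0 = SD²·(0.25 + 0.75r)
- R² = (0.25 + 0.75r)²/(0.375 + 0.625r)
- unadjusted SE = 0.25·√[(0.375 + 0.625r)·2/159]
- adjusted SE = unadjusted SE·√(1 − R²)

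| r | R² | SE unadjusted | SE adjusted | SE ratio |
|---|---|---|---|---|
| 0.4 | 0.484 | 0.0222 | 0.0159 | 0.72 |
| 0.5 | 0.568 | 0.0232 | 0.0153 | 0.66 |
| 0.6 | 0.653 | 0.0243 | 0.0143 | 0.59 |

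**Step 3: precision if T0 does not enter.** With QALY = 0.5·U1 + 0.5·U2, R² = r²/(0.5 + 0.5r). At r = 0.5 this is 0.25/0.75 = 0.333, an SE ratio of √0.667 = 0.82. At r = 0.4 and 0.6 the ratios are 0.88 and 0.74.

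**Step 4: what a mismatch can look like.** This is one data set, constructed to show the mechanism: r = 0.5, a utility gain of 0.03 at T1 and T2, a cost difference of 500 EUR, a cost SD of 8,000 EUR, and baseline utility one standard error lower in NET.

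- That standard error is 0.25·√(2/159) = 0.0280.
- The QALY gain is 0.75·0.03 = 0.0225. The imbalance moves the unadjusted difference by 0.625·0.0280 = 0.0175, leaving 0.0050.
- Unadjusted ICER: about 100,500 EUR/QALY (500 divided by the unrounded 0.00498).
- Adjusted: QALY difference 0.0233, cost difference 419 EUR, ICER about 18,000 EUR/QALY.
- At 100,500 EUR/QALY the adjusted curve stands at 0.84; the unadjusted curve stands at 0.50.

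The size of the gap reflects the imbalance imposed and the small denominator; it is not a forecast.

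**Step 5: what adjustment leaves.** Suppose the true QALY gain is 0.02. With the adjusted SE of 0.0143 to 0.0159, the range of ±1 SE still runs from 0.004-0.006 to 0.034-0.036. The ICER denominator remains fragile.

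**The case against.** The strongest reply has four parts.

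1. **Same target.** With 1:1 randomization and linear models, the unadjusted and adjusted differences estimate the same population difference, and the unadjusted one is unbiased with complete data. This stands. A reader might infer that the curve describes a different quantity, or that estimate and curve will contradict each other. The documents do not support either: the two estimates differ only by chance, and visibly only if a material imbalance occurs.

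2. **The adjusted ICER follows from planned output.** On the planned grid, adjusted net benefit at 0 EUR is minus the adjusted cost difference, and its slope is the adjusted QALY difference. This is true when the covariates are the same at every grid value. It shows that the fix is cheap, but it does not change which point estimate the plan reports.

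3. **Some regressions may be unadjusted.** The SAP synopsis plans a series of net-benefit regressions for uncertainty without mentioning adjustment, and SAP 8.1.3 lists uncertainty and adjustment as two purposes. A series with both kinds of model is a permissible reading. Baseline EQ-5D-5L is never named as a covariate. This too stands, and it makes the missing covariate list part of the point: the text does not say which models produce the curve.

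4. **Every economic figure above is assumed.** Correct. Deaths and the change from paper at T0 to telephone at T1 and T2 could lower the correlations, and the gain in Step 2 concerns QALYs only, not costs.

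The SAP's economic sensitivity analyses do not close the gap, because they address assumptions in calculating costs and benefits. The general remark in 8.1.3 about adjusted models for secondary outcomes does not mention the ICER.

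**Conclusion.** The point holds as one of precision and consistency, not of bias. The plan reports an ICER from unadjusted means and takes its uncertainty from regressions described as adjusting for unnamed covariates; the algebra of Step 1 shows that the two need not agree.

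On the stated assumptions, adjusting for baseline EQ-5D-5L lowers the standard error of the QALY difference by a factor of 0.59 to 0.72 if T0 enters by the trapezoid rule, and by 0.74 to 0.88 if it does not. The direction needs only a positive correlation between baseline utility and the QALY; the size depends on inputs that the documents do not give.

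A reader might also infer that adjustment would make the ICER stable. Step 5 shows that it would not: a ratio with a small denominator stays unstable under either estimator. The economic evaluation is secondary and exploratory, and the primary test and sample size are untouched. The change is worth making because it costs almost nothing.

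**What to change.** In SAP 8.1.3, Health economic evaluation:

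- Name the covariates: baseline EQ-5D-5L index, baseline CSSRI cost, and study site, by which randomization is stratified (protocol 9.1).
- Define the main ICER as adjusted incremental cost divided by adjusted incremental QALY, with the same covariates as the net-benefit regressions behind the acceptability curve.
- Report the unadjusted ICER beside it as a descriptive or sensitivity result.
- State how the T0 utility enters the QALY, since the gain from adjustment depends on it.

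This takes a few sentences. All the covariates are already recorded by the time of randomization, so no new data collection is needed.

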#### PICTURE Psychotherapy

For a qualitative evaluation of the PICTURE intervention, semi-structured interviews were conducted in a small subset of NET-participants with patients and GPs after T1. An estimated 10 to 15 interviews of patients and GP's, respectively and 3-5 expert interviews of supervising psychologists is needed for qualitative analysis. The sampling procedure was done in a systematic way trying to involve a broad range of aspects. On enrolling interviewees we aimed to include patients and GP's from urban and rural background, male and female gender, different age groups, patients of different social background and GP's in single and partner practices and with varying length of working experience. Transcribed interview data will be analyzed using thematic analysis to explore process and implementation experiences (Braun & Clark, 2006). The analytic process is structured and includes 6 defined phases (Phase 1: Becoming familiar with the data, Phase 2: Generating initial codes, Phase 3: Searching for themes, Phase 4: Reviewing themes, Phase 5: Defining and naming themes, Phase 6: Producing the report).

#### 8.1.4 Safety analysis

Safety analyses will be conducted for SAE reported during the trial period. The frequency of events and the possible relationship to the treatment condition will be analysed descriptively. The number and percentage of patients experiencing each SAE will be presented for each treatment arm. The number and percentage of occurrences of each SAE will also be presented for each treatment arm. No formal statistical testing will be undertaken. Data quality including potential underreporting will be discussed.

#### 8.2 Interim analysis

A fixed sample design was planned without confirmatory statistical testing for early decision making, and will be conducted as planned. There is no pre-planned efficacy interim analysis.

#### 8.3 Sample size calculation

We performed sample size calculations and additional simulations to detect a clinically relevant and empirically justified effect with respect to the PDS-5 total severity score (range 0-88 points). A detailed description of this process is given in the trial protocol. Based on these considerations, the achieved recruitment number of N=318 participants seems sufficient to satisfy the underlying assumptions of the sample calculations.

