#### 8.1.2 Analysis of the primary efficacy endpoint

Primary efficacy endpoint is the absolute change in the PDS total severity score from baseline at month 6 ( $\Delta_6$ PDS := PDST1 – PDST0). By default, the mode of administration is a self-administered paper-based version. For patients who did not complete and send back the paper-based patient questionnaire (non-responding survivors), the PDS-5 total score was assessed during the telephone survey T1, scheduled 6 months after randomization.

The null hypothesis H0:  $G_{NET}(x) = G_{iTAU}(x)$  and  $K_{NET}(t) = K_{iTAU}(t)$   $(0 < t \le T)$ 

is that the treatment groups NET and iTAU will not differ with respect to the distributions of the observed outcome measure  $\Delta_6 PDS$ , whereas  $G_i(x)$  is the cumulative probability distribution of the observed change in PDS severity scores at T1 in group i (i = NET or iTAU), and the distribution of times of death (most likely cause of missingness),  $K_i(t)$  is the cumulative distribution of informative event times in group i.

The null hypothesis will be tested using a two-sample t-test. The null hypothesis can be rejected if the two-sided *p*-value related to the test statistic for the treatment effect is equal to or smaller than the significance level  $\alpha$ =0.05 (two-sided).

Due to an expected high drop-out rate from death in critically ill patients, the nonparametric Lachin method was initially planned as the primary analysis, which is a modified version of the Wilcoxon-Mann-Whitney U-test with a worst rank approach for missing data. However, results from an interim report showed relatively low drop-out rates and a normal distribution of the main outcome variable ( $\Delta_6 PDS$ ). We have consequently decided to update the SAP, replacing the originally planned nonparametric test with a regular two-sample t-test. This change is made to align with the observed normal distribution characteristics of the main outcome variable. The t-test is more suitable for normally distributed data and will provide more accurate estimates of the treatment effect compared to nonparametric tests.

The principal analysis will be performed according to the intention-to-treat (ITT) principle, and unadjusted for screening or baseline covariates or site. The significance level is set to alpha = 5% (two-sided).

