15.3 Sample size calculation

We performed sample size calculations and additional simulations to detect a clinically relevant and empirically justified effect with respect to the PDS-5 total severity score (range 0-80 points).

Planning figures

Calculation of the reliable change index for previous NET trials indicates that a drop of about 25% (e.g. 23% in (Jacob, Neuner, Maedl, Schaal, & Elbert, 2014)) in the baseline score is a threshold that reflects a reliable change. To achieve mean baseline scores of about 40 points in this score, a mean change of at least $0.25 \times 40 = 10$ points would be necessary. Since post-ICU patients suffer from severe multiple medical conditions (SMOOTH data, (Schmidt et al., 2016)), a more conservative assumption of 60% was assumed for a minimum clinically important difference (MCID), resulting in a study arm mean difference of 6 points in PDS total score at T1.

A sample size of 131 patients (GPs) in each group (i.e., 262 patients in total) will have 80% power to detect a probability of 0.400 that an observation in Group NET is less than an observation in Group iTAU using a Wilcoxon (Mann-Whitney) rank-sum test with a 0.05 two-sided significance level (Software used: nQuery Advisor® 7.0).

The probability of $P(X_{\text{NET}} < X_{\text{iTAU}}) = 0.4$ was calculated with a presumed normal distribution – a difference in means ($\mu_{\text{iTAU}} - \mu_{\text{NET}}$) of 6 points and a common standard deviation of about 17 points – and an effect size of 0.36.

To address the properties of the complex (non-parametric worst rank score) analysis approach, we decided to randomize an additional 78 patients (+ ~30% (=39/131)). Thus, the sample size **to be allocated** to the trial is $N = 2 \times 170 = 340$ patients (GPs) in total.

In accordance with ICU/ regional study center commitments, 3000 patients can be screened, of which N=1000 (33%) are expected to show posttraumatic symptoms (Parker 2015). N=650 (65%) are expected to be willing to participate (patients and GPs) (SMOOTH: 20% non-participants; however, NET is more intense, therefore the rate of non-participation is expected to be higher in this trial), N=550 (~85%) to be screened by the treating GP 3 months post ICU (SMOOTH mortality after 6 months: 18%), N=400 (~70%) to meet inclusion criteria, and N=340 (85%) to consent to study participation at T0.

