We assume a 30% drop out rate from T0 to T1 (primary analysis), and a 15% drop out rate from T1 to T2 (secondary analyses).

Simulations to validate the results of the sample size planning:

Using Lachin’s strategy (Lachin, 1999) will result in analyses of all patients randomized. This is one intention of the ITT principle. However, this comes at the price of attrition due to missing values. To overcome this power-loss we have added another 30% to the original sample size. This choice was evaluated via a small simulation study by varying the number of patients per study arm to support our planning figures: for each setting we performed 10,000 replications and varied the study arm size from 100 to 170 per study arm (1:1 allocation). The results of the simulations to check for a sufficient sample size are displayed in the following figure:

[figure not shown]

Figure 2 Results of the simulations to validate the sample size planning.

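### SAP 8.3 calls N=318 sufficient on the protocol's assumptions, but with the t-test now planned and the protocol's 30% drop-out, 318 gives about 75-76% power; sufficiency depends on an observed drop-out rate that the SAP does not state

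*SAP*

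**What the plan says.** Protocol 15.3 gives the planning basis: "A sample size of 131 patients (GPs) in each group (i.e., 262 patients in total) will have 80% power" with a two-sided 5% Wilcoxon test, a 6-point difference, an SD of about 17 and a stated effect size of 0.36. To allow for the worst-rank analysis, "we decided to randomize an additional 78 patients", which gives 340. The same section says "We assume a 30% drop out rate from T0 to T1 (primary analysis") and explains that the worst-rank strategy "will result in analyses of all patients randomized". On the inflation it adds: "This choice was evaluated via a small simulation study by varying the number of patients per study arm to support our planning figures".

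SAP 8.1.2 changes the primary test, "replacing the originally planned nonparametric test with a regular two-sample t-test". One reason given is that "results from an interim report showed relatively low drop-out rates"; no rate follows. Weighting, mixed models and multiple imputation appear only as sensitivity analyses. SAP 4.1 reports 318 randomized against a target of 340. SAP 8.3 gives no power, required number or drop-out rate of its own. It refers to the protocol and concludes that "the achieved recruitment number of N=318 participants seems sufficient to satisfy the underlying assumptions of the sample calculations".

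**The concern.** The statement in SAP 8.3 rests on a calculation made for another test, another number randomized and a stated 30% drop-out. The worst-rank rule kept every randomized patient in the analysis. A t-test on the change score cannot use a patient without a T1 score unless a rule supplies one, and the SAP names none for the principal test. Drop-out therefore now reduces the analysed number directly, and the cited assumptions no longer lead to the stated conclusion.

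What is at stake is how a null or borderline result will be read. A reader of 8.3 would take it that the planned 80% power still holds. Whether it does depends on a figure that the SAP mentions but does not give.

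**Working it through.** **Inputs.** From protocol 15.3: two-sided alpha 0.05, 80% power, difference 6, SD about 17 (d = 6/17 = 0.353), stated d = 0.36, Wilcoxon probability 0.400, 131 per arm plus 39 per arm, 30% drop-out to T1. From SAP 4.1 and 6: 318 randomized, 1:1 allocation. From SAP 8.1.2: two-sample t-test. My assumption: patients without a T1 PDS-5 leave the principal test, in equal proportion in both arms.

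**1. The protocol's own figure reproduces.** Noether's formula for equal arms:

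N = (1.960 + 0.842)² / [12 × 0.25 × (0.5 − 0.4)²] = 7.849 / 0.03 = 261.6, or 131 per arm.

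The effect sizes agree with it: Φ(−0.36/√2) = 0.3995 and Φ(−0.353/√2) = 0.4015. Then 131 + 39 = 170 per arm, 340 in total.

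**2. Patients needed for 80% power by t-test.** With n per arm, power is the probability that a noncentral t with 2n − 2 degrees of freedom and noncentrality d√(n/2) exceeds the 5% two-sided critical value in absolute size.

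- d = 0.36: 123 per arm, 246 in total. 318 − 246 = 72 may be missing (22.6%).
- d = 6/17: 127 per arm, 254 in total. 318 − 254 = 64 may be missing (20.1%).

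The t-test's greater efficiency is already counted here. On the protocol's Wilcoxon figure of 262, the allowance is 318 − 262 = 56 (17.6%).

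**3. Power by missingness at T1.**

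| Randomized | Missing | With T1 score | Power, d = 6/17 | Power, d = 0.36 |
|---|---|---|---|---|
| 318 | 0% | 318 | 88.1% | 89.3% |
| 318 | 10% | 286 | 84.5% | 85.9% |
| 318 | 20% | 254 | 80.1% | 81.6% |
| 318 | 30% | 223 | 74.6% | 76.2% |
| 340 | 30% | 238 | 77.4% | 79.0% |

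**4. Where the gap at 30% comes from.** For 318 it is 80 − 74.6 = 5.4 points (d = 6/17) or 80 − 76.2 = 3.8 points (d = 0.36). Of this, 2.6 or 1.0 points would be there with 340 as well. The step from 340 to 318 adds about 3 (77.4 − 74.6 = 2.8; 79.0 − 76.2 = 2.8). With 30% missing, the t-test would need 123/0.7 = 175.7, so 176 per arm (352), or 127/0.7 = 181.4, so 182 per arm (364).

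**5. Sensitivity to the SD.** The range 6/17 to 0.36 reflects rounding only, and the SD is given as approximate. With a 6-point difference and the same method, SD 16.5 needs 240 patients (78 missing tolerated, 24.5%) and SD 17.5 needs 270 (48 missing, 15.1%). SDs that all round to 17 thus allow about 15% to 25% missing. At SD 17.5, the 254 patients left after 20% drop-out would not be enough.

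**6. The simulations.** They covered 100 to 170 patients per arm, a range that includes 159, but under the worst-rank strategy. I could not see their figure. By design they do not establish the power of a t-test.

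**The case against.** The strongest reply is that 30% missing is a scenario the SAP has already left behind. It reports low drop-out and gives that as a reason for changing the test. At 0% to 20% missing, the table shows 80% to 89% power. This stands: no shortfall is shown, and a reader who inferred that the trial is underpowered would go beyond the documents. But 8.3 rests on the protocol's considerations and does not cite the low drop-out, and without a rate one cannot tell 15% missing (84.5 − 2.1 = about 82% or more at the protocol's effect size) from 25% (below 80%).

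A second reply is that 8.3 speaks of assumptions and not of 80% power, and that 318 exceeds the calculated 262 by 56. That is a fair reading if drop-out is below 17.6%; it does not meet the 30% stated in the same protocol section.

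Third, leaving out patients without a T1 score is an assumption. The SAP synopsis still lists 318 to be analysed, its null hypothesis refers to patients with and without missing scores, and SAP 8.6 promises use of all available data. None of these supplies a value for a missing T1 score, so the assumption is the natural one, but the documents do not state it.

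A reader might also blame under-recruitment. The documents support that only in part, since 340 would miss 80% too. Nor is the protocol's sum wrong: 262 reproduces.

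Finally, recruitment is closed, so no sample size decision remains, and the planned dropout analysis (SAP 8.1.1) will show the rate. That limits the weight of the point, but 8.3 still makes a claim that should be supported.

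**Conclusion.** On the assumptions that SAP 8.3 cites, the claim does not hold: with 30% missing at T1, 318 gives 75-76% power for the planned t-test, and 340 would give 77-79%. This rests on analysing only patients with a T1 PDS-5, equal missingness in both arms, and an effect of 6/17 to 0.36.

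The fault is an unsupported statement that was not updated when the test changed. On the drop-out actually seen, 318 may well be enough: at the protocol's effect size it keeps 80% power up to 20-23% missing, or 15-25% if the SD lies between 16.5 and 17.5. The SAP should be corrected on this point, but nothing here puts the planned analysis itself in doubt.

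**What to change.** In SAP 8.3, replace the sentence that contains "the achieved recruitment number of N=318 participants seems sufficient to satisfy the underlying assumptions of the sample calculations" with a conditional statement:

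- 80% power for the two-sample t-test needs about 250 patients with a T1 PDS-5 (246 at d = 0.36, 254 at 6/17; 240 to 270 for an SD of 16.5 to 17.5).
- With 318 randomized, power is 88-89% at 0% missing, 85-86% at 10%, 80-82% at 20% and 75-76% at 30% (d = 6/17 to 0.36).
- 318 does not give 80% power at the protocol's 30% drop-out. Sufficiency rests on the observed T1 missing rate, pooled over arms, and that rate is quoted.
- The figures assume that patients without a T1 score do not enter the principal test; if another rule is intended, name it.

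The rate should come from a count pooled over arms. SAP 8.1.2 does not say whether the interim report was pooled or blinded, so its rate should be quoted only if it was. If the visit windows were kept, the count should be close to final: patients randomized by 31 December 2022 reach T1 within 6 months plus 3 weeks of T0, which is by late July 2023, the month of the SAP.

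The cost is a few sentences and one pooled count. No change of test and no extra patients are needed. Done before the groups are compared, it sets the yardstick in advance.
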